7. DEMOGRAPHICS, BASELINE CLINICAL CHARACTERISTICS, AND MEDICAL AND TREATMENT HISTORIES

Summaries for the demographics and baseline characteristics will be produced for the safety and ITT populations individually. Summaries of medical history and prior therapies and medications will be produced for subjects in the ITT population. Individual subject listings will be provided to support summary tables.

7.1. Demographic and Baseline Clinical Characteristics

Subjects' age, height, weight and other baseline continuous characteristics (e.g., vital signs, laboratory data) will be summarized with summary statistics (n, mean, standard deviation, median, minimum and maximum), while gender, ethnicity, race, and other baseline categorical characteristics [e.g., age category (<65 vs. ≥ 65), electrocardiogram (ECG) interpretation, Eastern Cooperative Oncology Group (ECOG) performance status] will be reported using frequency tabulations showing frequency and corresponding percentages. Baseline is defined as the last measurement before the first dose of the IP (or the last measurement before enrollment in case the first dose date is missing). When there are retested values, the retest values will be used for the analysis.

Stage of MM and duration in years of MM will be summarized descriptively. Serum and urine heavy chain type, light chain type, and type of light chain disease from immunofixation will be tabulated descriptively. Presence of bone lesions, presence of plasmacytoma, development of hypercalcemia, increasing Myeloma paraprotein will be tabulated descriptively.

7.2. Medical History

Medical and surgical history will be coded using the Medical Dictionary for Drug Regulatory Activities (MedDRA) Version 15.0 or higher. System organ class and preferred term will be summarized by frequency and percentage. Prior Anti-myeloma Therapies, Radiotherapy, and Surgeries.

Prior anti-myeloma drugs will be summarized using frequency tabulations by preferred term [World Health Organization (WHO) dictionary term version in use at the time of analysis]. A summary of last prior anti-MM drugs (i.e., drugs included in the last anti-MM regimen prior to study entry) will also be produced.

Exposure (Y/N) to selected prior anti-MM therapies and regimens and refractory (Y/N) to selected prior anti-MM drugs and regimens will also be summarized using frequency tabulations.

Prior anti-MM drugs will also be classified to one of the following drug classes and tabulated: Immunomodulatory compounds, Proteasome inhibitors, Corticosteroids, Alkylators, Anthracyclines, Nitrosoureas, Alkaloids, Platinum, and other novel agents.

Evidence of disease progression on the last lenalidomide-containing regimen, evidence of disease progression the last Bortezomib-containing regimen and evidence of the most recent disease progression (i.e., progression on the last treatment if it did not include lenalidomide and/or Bortezomib).

7.3. Prior Medications

Prior medications are defined as medications that were started before the start of the study treatment (regardless whether or not ended before the start of the study treatment). Prior medications that continue into study treatment period will also be reported as concomitant therapy.

All prior medications will be summarized in frequency tabulations. The Anatomical Therapeutic Chemical (ATC) coding scheme of the WHO dictionary term (according to the version in use at the time of analysis) will be used to group medications into relevant categories for these tabulations.

7.4. Other Medical History related to Refractory or Relapsed and Refractory Multiple Myeloma

Prior venous thromboembolic events, prior cancer history and corresponding treatments will be summarized with summary statistics or frequency distributions, as appropriate.

7.5. Cytogenetic Analysis

Subjects will be considered as having a 'modified high risk' cytogenetic profile if having either a 17 p Deletion or t(t;14) translocation abnormality based on adequate cytogenetic sample(s).

Subjects will be considered as having a 'standard risk' cytogenetic profile if having neither a 17 p Deletion nor a t(t;14) translocation abnormality based on adequate cytogenetic sample(s).

The cytogenetic sub-group analysis will be provided in a separate report.

8. STUDY TREATMENTS AND EXTENT OF EXPOSURE

Treatment duration, cumulative dose, dose exposure, average daily dose, relative dose intensity, and dose modification will be assessed separately for POM and LD-DEX as well as combined. Summary statistics will be reported for treatment duration, cumulative dose, dose exposure, average daily dose, dose intensity, relative dose intensity, and dose modification/interruption.

8.1. Treatment Duration

The treatment duration (weeks) is defined as:

$$[(\text{last cycle end date}) - (\text{date of the first study drug administration}) + 1] / 7$$

where 'last cycle end date' is defined in section 4.1.3: Calculation of Cycles, in this document. Summary statistics will be provided for treatment duration for overall treatment (i.e., either pomalidomide or dexamethasone, whichever is earliest for the 'date of the first study drug administration' and whichever is later for the 'last cycle end date'), as well as for pomalidomide and dexamethasone separately.

Additional summaries will be created for all treated subjects, displaying number of subjects treated by the number of cycles administered.

8.2. Cumulative Dose

Cumulative dose is defined as the sum of all doses taken across the treatment period (in milligrams) and will be calculated for pomalidomide and dexamethasone separately.

8.3. Dose Exposure

Dose exposure in days is defined as the total number of actual days on drug during the treatment period and will be calculated for pomalidomide and dexamethasone separately.

8.4. Average Daily Dose

Average daily dose will be calculated as the cumulative dose divided by dose exposure and will be calculated for pomalidomide and dexamethasone separately.

8.5. Dose Intensity

The delivered dose intensity (DDI) is defined as the cumulative dose delivered divided by the treatment duration and will be calculated for pomalidomide and dexamethasone separately.

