4.1.3. Calculation of Cycles

The start date of each treatment cycle will be calculated based on study drug exposure records for each subject. The start date of the first cycle will be the date when the subject receives any study drug.

Once the start dates, e.g., S_1, S_2, S_3, \dots are calculated, the end date of each cycle is calculated as the day before the start date of the following cycle, i.e., $E_i = S_{i+1} - 1$. For the last cycle, the end date (if missing or less than 28 days after start of cycle) will be calculated as the start date plus the prescribed cycle length (28) - 1, or the death date, or the discontinuation date, whichever is earlier.

The cycle number for each date of interest, e.g., AE or lab, will be calculated based on the cycle window set by their start and end dates. If a date is on or after S_i and before S_{i+1} , the corresponding cycle number will be cycle i .

Once the cycles are derived, they can be used to attribute adverse events to a specific cycle based upon the following rules: the start date of the adverse event should be included in a given cycle or if the start date does not fit in any defined cycle, the adverse event will be attributed to the previous cycle if the AE has started within 28 days after the end of the cycle.

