6. SUBJECT DISPOSITION

A summary of subject disposition (analysis population allocation, subjects entered, subjects discontinued, along with primary reason for both IP and study discontinuation) will be presented for each of the analysis populations (ITT Population and Safety Population) and will be summarized using frequency and corresponding percentage.

Reasons for discontinuing the IP will be collected on the CRF and will be summarised for all subjects with the following categories possible:

- Death
- Adverse event
- Pregnancy
- Progressive disease
- Lack of efficacy
- Recovery
- Withdrew consent
- Non-compliance with the study drug
- Lost to follow-up
- Study terminated by sponsor
- Transition to commercially available treatment
- Protocol violation (specify)
- Other (specified)

Among those who discontinue the IP, the number of subjects who then discontinue from the study versus those that enter follow-up will be summarised.

Reasons for discontinuing the study will be collected on the CRF and will be summarized for all subjects with the following categories possible:

- Screen failure
- Death
- Adverse event
- Pregnancy
- Progressive disease

- Lack of efficacy
- Recovery
- Withdrew consent
- Non-compliance with the study drug
- Lost to follow-up
- Study terminated by sponsor
- Transition to commercially available treatment
- Protocol violation (specify)
- Other (specified)

A summary tabulation will be provided for subjects enrolled by study center. Duration of study participation, defined as the time from IVRS enrollment date to IP discontinuation date (or the date of last visit for subjects still receiving the IP at the time of study close), will be summarized.

A separate listing will be provided for subjects who have signed consent but are not enrolled because of not meeting all inclusion/exclusion criteria (i.e., screen failure subjects). The reasons for screen failure will be tabulated.

Protocol deviations and violations will be presented in a data listing and summarized by categories in summary tables per deviation/violation type using frequency and corresponding percentage of occurrence.

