8.6. Relative Dose Intensity

The relative dose intensity (RDI) is calculated as the DDI divided by the planned dose intensity (PDI) whereby the DDI is calculated as the total dose delivered divided by the total time to complete the delivery:

- For POM, the PDI is $(4*21)/28 = 3$ mg per day.
- For LD-DEX, the PDI is $(40*4)/28 = 160/28$ mg per day for subjects ≤ 75 years old and $(20*4)/28 = 80/28$ mg per day for subjects > 75 years old.

The RDI will be calculated for pomalidomide and dexamethasone separately

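### As written, relative dose intensity divides mg per week by mg per day, so it comes out seven times too large

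*SAP*

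**What the plan says.** Four statements in the SAP have to be read together.

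- Section 8.1: "The treatment duration (weeks) is defined as" the last cycle end date minus the first dose date, plus 1, all divided by 7. The division by 7 is part of the formula.
- Section 8.2 gives cumulative dose in milligrams.
- Section 8.5: "The delivered dose intensity (DDI) is defined as the cumulative dose delivered divided by the treatment duration", separately for each drug. No unit is given for the result.
- Section 8.6 sets RDI as DDI over PDI. The PDI is 3 mg per day for pomalidomide, 160/28 mg per day for dexamethasone up to age 75, and 80/28 "mg per day for subjects > 75 years old". The same sentence restates the denominator of the DDI: "the DDI is calculated as the total dose delivered divided by the total time to complete the delivery". That time has no definition and no unit, and the SAP does not say that it equals the treatment duration of Section 8.1.

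**The concern.** The numerator of the RDI inherits weeks from Section 8.1, and the denominator is stated per day in Section 8.6. No step converts one to the other. An RDI programmed from the text therefore cannot be read as a percentage of planned dose.

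What is at stake is limited. Section 8 asks for summary statistics of the RDI, and these show how much of the planned dose was delivered when the safety results are read. No hypothesis test uses them. Cumulative dose, dose exposure in days and average daily dose do not involve treatment duration and are unaffected. The DDI in mg per week is a legitimate quantity in itself; the ratio is what fails.

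The second description of the DDI in Section 8.6 adds a smaller problem. Whoever corrects the unit finds two wordings for one denominator, and only one of them leads to a defined variable.

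**Working it through.** **Inputs.** Planned dose per 28-day cycle, from the PDI expressions in Section 8.6: pomalidomide 4 × 21 = 84 mg; dexamethasone 40 × 4 = 160 mg (age 75 or under) and 20 × 4 = 80 mg (over 75). One complete cycle lasts 28 days (Section 4.1.3), so treatment duration under Section 8.1 is 28/7 = 4 weeks.

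**The plan's own PDI figures.** 84/28 = 3.000, 160/28 = 5.714 and 80/28 = 2.857 mg per day. All three reproduce.

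**RDI as written, one full-dose cycle.** RDI = [cumulative mg / weeks] / PDI per day.

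- Pomalidomide: (84/4)/3 = 21/3 = 7.0, or 700%.
- Dexamethasone, 75 or under: (160/4)/5.714 = 40/5.714 = 7.0, or 700%.
- Dexamethasone, over 75: (80/4)/2.857 = 20/2.857 = 7.0, or 700%.

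**General case.** For a cumulative dose of D mg over n days, [D/(n/7)]/PDI = 7 × (D/n)/PDI. The factor is exactly 7 whatever the number of cycles or the dose taken. A check at 1, 2 and 6 full cycles gave 7.0 each time.

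**Reduced dose.** Half the planned pomalidomide dose in one cycle: (42/4)/3 = 3.5, or 350%, where the correct value is (42/28)/3 = 0.50, or 50%. The literal RDI falls to 100% only at 12 mg of the 84 mg planned: (12/4)/3 = 1.0.

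**With both terms per day.** Pomalidomide (84/28)/3 = 1.0; dexamethasone (160/28)/(160/28) = 1.0 and (80/28)/(80/28) = 1.0. Each full-dose cycle reads 100%.

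**The case against.** The strongest reply is that days are plainly intended. Section 4.1.2 calculates intervals in days and treats weeks as a presentation unit, so the division by 7 in Section 8.1 can be seen as that conversion. Section 8.5 names no unit, and only a daily DDI makes sense against a daily PDI. A programmer who saw 700% would correct it. Most of this stands, and it is why the point is minor. It does not remove the error: Section 8.1 puts the 7 inside the definition of treatment duration, and Section 8.5 uses treatment duration by name.

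On the restatement in Section 8.6, the reply is that it is loose wording for the same quantity. That is the more likely reading. A reader might instead take it as the span from first to last dose and infer an inflated RDI that would pass unnoticed. If pomalidomide is assumed to be taken on consecutive days 1 to 21, complete full-dose cycles would give 84/21/3 = 133% after one cycle, 168/49/3 = 114% after two and 504/161/3 = 104% after six. The SAP supports neither step: it does not define the time that way and names no dosing days. The reading also fits poorly with a PDI that spreads the cycle's dose over all 28 days. What remains is a redundant, undefined clause.

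**Conclusion.** Wrong as written; minor. Read together, Sections 8.1, 8.5 and 8.6 overstate the RDI by a factor of exactly 7 for both drugs. The result assumes only that the DDI of Section 8.5 is the one carried into the RDI, because the Section 8.6 version has no unit. The error would probably be noticed at first output, and it reaches only the descriptive RDI summaries. The undefined restatement in Section 8.6 is an editorial fault with no demonstrated numerical effect.

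A reader might also infer that treatment duration itself is unsettled, because Section 4.1.3 ends the last cycle at "the start date plus the prescribed cycle length (28) - 1, or the death date, or the discontinuation date, whichever is earlier" without saying whether IP or study discontinuation is meant. That is not part of this point. Section 4.1.3 builds cycles from study drug exposure records, and Section 3.1 starts follow-up at permanent IP discontinuation, so the context largely settles it as IP discontinuation. Any remaining doubt would also concern the treatment duration summary, the attribution of adverse events to cycles and the PFS window, and so would not be a question about the RDI alone.

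**What to change.** 1. In Section 8.5, define the DDI once: cumulative dose (mg) divided by treatment duration in days, that is, last cycle end date minus first dose date plus 1, reported in mg per day.
2. In Section 8.6, delete the clause that restates the DDI. Keep RDI = DDI/PDI and the PDI values as they are.

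Section 8.1 can continue to report treatment duration in weeks. The cost is two wording changes and the unit of one derived variable. No new data are needed, and no dose or clinical rule changes.

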8.6. Relative Dose Intensity

The relative dose intensity (RDI) is calculated as the DDI divided by the planned dose intensity (PDI) whereby the DDI is calculated as the total dose delivered divided by the total time to complete the delivery:

- For POM, the PDI is $(4*21)/28 = 3$ mg per day.
- For LD-DEX, the PDI is $(40*4)/28 = 160/28$ mg per day for subjects ≤ 75 years old and $(20*4)/28 = 80/28$ mg per day for subjects > 75 years old.

The RDI will be calculated for pomalidomide and dexamethasone separately

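### RDI can exceed 100% at the planned dose when the last cycle is cut short, because the planned intensity stays a full 28-day average

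*SAP*

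**What the plan says.** Four sections of the SAP combine.

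- **Section 8.6** divides delivered dose intensity (DDI) by planned dose intensity (PDI). The PDI is a constant per drug: "For POM, the PDI is $(4*21)/28 = 3$ mg per day". For dexamethasone, "For LD-DEX, the PDI is $(40*4)/28 = 160/28$ mg per day for subjects" up to 75 years of age, and 80/28 above that age. Both constants include the days of the cycle without drug.
- **Section 8.5** gives the numerator of RDI: "The delivered dose intensity (DDI) is defined as the cumulative dose delivered divided by the treatment duration".
- **Section 8.1** runs treatment duration from the first administration to the last cycle end date, "where 'last cycle end date' is defined in section 4.1.3: Calculation of Cycles, in this document".
- **Section 4.1.3** fixes that end date. If it is missing or falls short of the 28 days, it "will be calculated as the start date plus the prescribed cycle length (28) - 1, or the death date, or the discontinuation date, whichever is earlier".

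Section 8.6 also words the DDI a second way: "the DDI is calculated as the total dose delivered divided by the total time to complete the delivery". It does not define that time further. No section prorates the PDI for an incomplete last cycle, caps RDI, or says how a value above 100% should be read.

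**The concern.** The two sides of the ratio cover different stretches of time. If the dosing days come first in the cycle, a subject who dies or stops part-way has taken the early doses. The drug-free days that would have followed are cut from treatment duration but remain averaged into the PDI. The ratio then rises above 100% although no dose exceeded the plan.

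RDI should show how much of the planned regimen was delivered. The study's primary objective is safety, and POM exposure is a listed secondary endpoint. The distortion is largest in subjects with little time on treatment, where delivered dose is of most interest. Section 4 calls for the mean and maximum among the default statistics, and both respond to such values.

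**Working it through.** **Inputs from the SAP.** POM 4 mg on 21 of 28 days; LD-DEX 40 mg (20 mg above 75 years) on 4 of 28 days (Section 8.6); the end-date rule (Section 4.1.3).

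**Assumptions, not in the SAP.**
- POM is taken on days 1–21 and LD-DEX on days 1, 8, 15 and 22. The SAP gives only the counts.
- The discontinuation date is that of the IP and coincides with the stop day.
- All planned doses up to that day are taken.
- Duration is in days. Section 8.1 states weeks, which is a separate unit question.

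**Step 1: the plan's own figures.** POM: 4 × 21 / 28 = 3 mg per day, reproduced. LD-DEX: 160/28 = 5.714 and 80/28 = 2.857 mg per day.

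**Step 2: RDI under the plan's rules.** For n full cycles and a last cycle ending on day d:

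- POM RDI = (84n + 4 × min(d, 21)) / (28n + d) / 3
- LD-DEX RDI = (160n + 40 × doses due by day d) / (28n + d) / (160/28). The ratio is the same for the 20 mg group.

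**Step 3: POM results.**

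| Full cycles before | Last cycle ends on | Calculation | RDI |
|---|---|---|---|
| 0 | any day up to 21 | 4 / 3 | 133.3% |
| 0 | day 24 | 84 / 24 / 3 | 116.7% |
| 0 | day 28 | 84 / 28 / 3 | 100% |
| 1 | day 21 | 168 / 49 / 3 | 114.3% |
| 2 | day 21 | 252 / 77 / 3 | 109.1% |
| 4 | day 21 | 420 / 133 / 3 | 105.3% |

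**Step 4: LD-DEX results, first cycle.** The ratio peaks on dosing days and falls back between them.

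- Day 1: 40 / 1 / 5.714 = 700%
- Day 8: 80 / 8 / 5.714 = 175%
- Day 15: 120 / 15 / 5.714 = 140%
- Day 22: 160 / 22 / 5.714 = 127.3%
- Days 7, 14, 21 and 28: exactly 100%

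**Step 5: a reduced dose.** At 3 mg POM for 21 days with a stop on day 21 of cycle 1, RDI = 63 / 21 / 3 = 100%.

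**Step 6: cases that do not exceed 100%.**

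- 2 mg POM, stop on day 14 of cycle 1: 28 / 14 / 3 = 66.7%
- Full dose, last dose on day 14, discontinuation recorded on day 21: 56 / 21 / 3 = 88.9%
- Full dose, 7-day delay before cycle 2, stop on its day 14: (84 + 56) / (35 + 14) / 3 = 95.2%

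**Step 7: the second DDI wording.** If the time to complete delivery means first to last dose, even one complete POM cycle gives 84 / 21 / 3 = 133%. That reading does not remove the problem.

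**The case against.** The strongest reply is that this is a narrow artefact in one descriptive statistic. Much of that stands.

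- A reader might infer that every subject who stops mid-cycle scores above 100%. The documents do not support that. It takes near-full dosing, little earlier delay, and a discontinuation date soon after the last dose; Step 6 shows the opposite outcome in each respect.
- A reader might infer that a dose reduction in the only cycle disappears from the report. It disappears from RDI alone. Average daily dose (Section 8.4) would show 63 / 21 = 3 mg in the Step 5 example. Section 8.7 and the dose-reduction tables in Appendix B would also show the reduction.
- A reader might take 700% as typical for LD-DEX. It is the extreme, for a stop on the first dosing day.
- The SAP does not say how many subjects stop early or why, so the overall effect on the mean cannot be computed, nor can it be said that toxicity drives it. For each 1% of subjects who stop by day 21 of cycle 1 at full POM dose, the mean rises by 0.01 × 33.3 = 0.33 percentage points compared with scoring them 100%. The median, also reported, is less sensitive.
- Section 4.1.3 does not say whether IP or study discontinuation is meant, although Section 6 separates the two. On the study reading, the cut would occur less often.

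These limits narrow the point but do not remove it. The stated rules still give a fully compliant early stopper an RDI above 100%, and nothing in the SAP corrects or explains it.

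**Conclusion.** The point holds as a conditional one: under the stated rules, RDI *can* exceed 100% at the planned dose when the last cycle is cut short. For POM the excess is at most 33 percentage points and shrinks as full cycles accumulate. For LD-DEX it ranges from nil to very large, depending on the stop day. The sizes rest on the assumed dosing days, the IP reading of the discontinuation date, and units in days.

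It would be too strong to say that the safety conclusions are affected. The primary endpoint is adverse event incidence, and RDI enters no planned adverse event, efficacy or sample-size calculation. The correction is still worth making, because the summary is distorted most in early stoppers and the change is small.

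**What to change.** In Section 8.6, keep the fixed PDI for completed cycles, so that cycle delays still lower RDI. Change only the treatment of a last cycle that is cut short:

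RDI = cumulative dose / (PDI × days in completed cycles + dose scheduled in the last cycle up to its end date)

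The scheduled dose should use the dose levels already in the PDI and the dosing days in the protocol. Checks:

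- Compliant POM stop on day 21 of cycle 1: 84 / 84 = 100%.
- The 3 mg example: 63 / 84 = 75%.
- A 35-day first cycle and a full second cycle: 168 / (3 × 35 + 84) = 168 / 189 = 88.9%, the same as now (168 / 63 / 3).
- The 7-day delay with a day-14 stop in cycle 2: 140 / (105 + 56) = 87.0%, against 95.2% now.

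In Section 4.1.3, state whether the discontinuation date is that of the IP or of the study.

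Extending every last cycle to 28 days is not a good substitute. It would score a compliant day-14 stopper 56 / 84 = 67%, and so count early stopping, and days after death, as lost intensity.

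The cost is slightly more programming and somewhat lower reported RDI values. No new data are needed, and no dose or schedule changes.
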